Metformin is the most widely prescribed anti-diabetes medication in the world and the first-line therapy for treating type 2 diabetes (T2D) in youth and adults. However, metformin's glucose-lowering ability is variable in clinical practice, and efficacy is further limited by poor medication adherence because of metformin-associated adverse effects. Gastrointestinal (GI) symptoms such as bloating, abdominal discomfort, cramping, and diarrhea are the most common side effects associated with metformin use occurring in up to 80% of individuals at drug initiation and up to 30% in individuals on chronic treatment. In youth with type 2 diabetes, the burden of metformin-associated side effects is high because metformin is the only oral FDA-approved for treatment and there are no other oral alternatives. Therefore, identifying ways to mitigate these GI side effects, especially in youth with type 2 diabetes, is of high clinical significance. New data suggest that metformin-induced changes in the gut and/ or the microbiome may be related to both its beneficial (glucoselowering) and adverse effects. To address this clinical challenge, prebiotic fibers that are non-digestible food ingredients, may help to improve metformin tolerability by increasing beneficial bacteria and stool metabolites, such as short chain fatty acid (SCFA) stool concentrations. This pilot study will test the hypothesis that a prebiotic microbiome modulator (MM) – containing prebiotic fibers and polyphenols – will reduce GI side effects of metformin at time of initiation and change the stool metabolite profile in youth and young adults with T2D treated with metformin, age 10-25 years who are not on insulin therapy. The 9-week study will have 2 phases and 6 outpatient visits at the NIH Clinical Center. Phase 1 is a 5-week randomized double blind cross-over trial with two 1-week intervention periods (metformin + prebiotic and metformin + placebo) during which subjects will eat a standardized diet. Phase 2 will occur immediately following phase 1 in which participants will start an open-label 4-week intervention with metformin and the prebiotic MM.

1.0 Background

Metformin is the most widely prescribed anti-diabetic agent in the world and is first line for treatment of type 2 diabetes (T2D) in both adults and children [1, 2]. However, metformin non-responsiveness is an important clinical challenge, occurring in 20-50% of youth and adults [3], and reduced treatment adherence is a well-recognized and potentially modifiable risk factor [4]. Metformin related gastrointestinal (GI) side effects (bloating, diarrhea, cramping, nausea and

[figure not shown]

[figure not shown]
Figure 1Potential mechanisms of metformin-related changes in gut metabolites and lower GI side effects. H2S: hydrogen sulfide, GLP-1: glucagon-like peptide 1,FXR: farnesoid X receptor (References: 14-16)

vomiting) are a common barrier to maximal dose escalation and treatment optimization [5]. These side effects are also a frequently reported reason for non-adherence [5]. Side effects are observed in > 80% of individuals newly initiated on metformin and ~10-30% of patients on long-term therapy [6, 7], with estimates of 1 in 4 youth taking metformin having at least one GI side effect [8]. Challenges are magnified in youth with T2D, as metformin is the only oral medication that is approved for use in the 10-17-year age group. Yet, there is a paucity of studies examining the mechanisms of metformin's GI side effects in vivo, and thus limited ability to mitigate these

Last updated: February 9, 2021

issues. This pilot study, a randomized double-blind crossover trial, examines the use of a prebiotic as an adjunct to improving metformin tolerability, facilitating short-term dose escalation, and also explores the underlying gut-based mechanisms of both metformin action and intolerance in youth and young adults with type 2 diabetes.

Metformin-induced changes in the microbiome are emerging as an important primary mechanistic target. Initial studies in adults suggest that short-term metformin therapy increases production of short chain fatty acids (SCFAs) and incretins (glucagon-like peptide-1 [GLP-1] and peptide YY [PYY]) [9, 10] by increasing populations of SCFA-producing bacteria, such as *Akkermansia muciniphila* and *Bifidobacterium adolescentis* [11-13]. However, other changes in the gut milieu may also contribute to the adverse GI side effects commonly seen with metformin use, but few studies have resolved the cellular mechanisms that cause of metformin's GI side effects. Figure 1 illustrates three (3) hypothetical mechanisms of metformin-induced changes in the gut microbiome that may contribute to its GI symptoms. For example, metformin-induced inhibition of colonic bacterial glycerophosphate dehydrogenase increases colonic lactate acidosis that may be toxic to the gut mucosa [14]. Alternatively, high concentrations of stool bile acids, secondary to direct farnesoid X receptor (FXR) inhibition by metformin, may cause osmotic diarrhea [15]. Additionally, metformin-treated patients have increased abundance of *Escherichia sp* that was associated with functional shifts with enrichment of virulence factors and gas metabolism genes, specifically for the production of hydrogen sulfide gas [16].

While the precise mechanism of metformin-induced GI side effects remains to be elucidated, microbiomeinfluencing supplements may benefit patients with diabetes. Even without other medications, prebiotic fiber has been shown to improve the metabolic profile in patients with and without diabetes [17-19]. Prebiotics are substrates for bacterial fermentation and SCFA production (Figure 2) and are defined as "nondigestible food ingredients that beneficially affect the host by selectively

Figure 2- Proposed Mechanism of Prebiotic Microbiome Modulator, adapted from [25]

stimulating the growth and/or activity of one or a limited number of bacteria in the colon, thus improving host health" [20]. These supplements are effective in reducing the severity and duration of infectious diarrhea [21], as well as improving bowel regularity. Prebiotics may also improve intestinal permeability and gut inflammation - two factors which have been linked to obesity and metabolic syndrome [22, 23]. However, prebiotic supplements, when used in isolation, could increase flatulence by producing methane and hydrogen sulfide gas as byproducts via methanogen and sulfate-reducing bacteria, respectively (Figure 2) [24]. To decrease these unwanted side effects, preliminary studies have demonstrated that using polyphenols -- naturally occurring compounds that are metabolized by the SCFA-producing bacteria (acetogens)-- may be helpful in reducing flatulence (Figure 2) [25]. The presence of polyphenols, commonly found in fruits and vegetables, allows acetate-producing bacteria to thrive, while methane- or hydrogen sulfate-producing bacteria have less available hydrogen substrate to convert to their respective gases [25, 26]. In a pilot randomized trial of 10 adults with T2D, a prebiotic microbiome modulator (MM) with inulin and beta glucan plus polyphenols from blueberry pomace improved metformin tolerability and fasting glycemia [27]. This same cocktail improved glucose profiles in healthy adults with overweight and obesity during an oral glucose tolerance test [28]. However, the mechanisms by which prebiotics influence metformin-induced GI side effects are unknown. Importantly, it remains to be established whether using this supplement is feasible in youth and young adults with T2D, whose microbiome signatures may be different from adults [29]. This study is innovative and clinically significant because it uses a prebiotic intervention to evaluate gut-incretin pathways while identifying whether a relatively safe supplement could

improve quality of life and glycemia in youth and young adults with type 2 diabetes who are high-risk for diabetesrelated complications.

Preliminary studies:

Currently, we are exploring metformin's mechanism of action in African American youth with T2D (NCT02960659), including changes in their microbiome. Our preliminary findings from 4 youth who were evaluated before and after 3-months of metformin therapy showed a decreasing trend for HbA1c (-0.56±0.2%) and increasing trends for stool

[figure not shown]

Figure 3. Stool short Chain Fatty Acid Concentrations in feces before and after 3 months of metformin therapy in youth with type 2 diabetes (n=4).

propionate and butyrate (P=0.1, Figure 3). In collaboration with [name] at Wake Forest, using 16S Ribosomal targeted sequencing and Qiime analysis of Operational Taxonomic Units (OTUs), we also observed modest changes in microbial diversity, a decreasing trend in the Shannon index (an index of complexity, P=0.15). This decreased diversity has been seen in other studies of metformin-induced changes in the gut

microbiota [14]. Therefore, metformin may change gut microbial diversity in association with changes in SCFA stool concentrations in youth, but larger samples sizes are needed

for confirmation. While metformin alone can increase SCFA, prebiotic MM may be able to augment this increase by shifting substrate metabolism away from gas (hydrogen sulfide and methane) to acetate production. Further investigations into these mechanisms will help us determine the feasibility of an oral supplement to mitigate side effects of metformin and improve quality of life, as well as glycemia, in youth with T2D.

2.0 Specific Objectives/ Aims

The primary objective of this study is to determine the feasibility and efficacy of a prebiotic MM to improve metformininduced lower GI side effects in youth with T2D and the secondary objective is to measure the change in stool SCFA content after prebiotic MM intervention.

Aim 1. To compare lower-GI side effects and stool consistency (tolerability score) in youth and young adults with T2D at initiation of daily metformin therapy when used with a daily prebiotic microbiome modulator (MM) vs placebo over a 1-week period.

Hypothesis: A prebiotic MM will be associated with higher tolerability scores (a composite score of lower GI-related side effects and stool consistency) compared to placebo.

Rationale: A prebiotic MM, containing both fiber and polyphenols, reduced metformin-related GI side effects in adults with T2D while retaining, and even augmenting, the hypoglycemic effects expected with metformin therapy in a small study (4). Due to the significant potential for clinical benefit, we propose to validate these results in youth, in whom metformin is the only FDA approved anti-diabetic therapy.

Aim 2. To compare the change in SCFA stool content in youth with T2D on metformin therapy when treated with prebiotic MM vs. placebo after 1 week and 4 weeks.

Hypothesis: The prebiotic MM will be associated with higher SCFA stool content compared to placebo. **Rationale**: SCFAs are microbial metabolites derived from fermentation of dietary fibers that are likely gut mediators of glucose metabolism. Metformin and prebiotic fiber individually have been demonstrated to increase stool SCFA [13, 16, 30, 31]. We propose to further elucidate the mechanism of metformin and MM, both individually and when taken together. **Exploratory aims:** To evaluate the relationship of change in tolerability score with change in stool SCFA, change in gut microbial diversity and SCFA-producing phyla, change in intestinal permeability markers, determine tolerability score for metformin and prebiotic MM over 1 month, and change in measures of glucose, insulin and incretin kinetics after treatment with placebo compared to 4 weeks of continuous prebiotic MM intervention.

[figure not shown]

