3.0 Study Design

3.1 Study Design and Timeline

This 9-week pilot study will have 2 phases and 6 outpatient visits at the NIH Clinical Center (Figure 4). Phase 1 is a 5week randomized double-blind randomized cross-over trial with two 1-week intervention periods (metformin + prebiotic and metformin + placebo). Phase 2 will occur immediately following phase 1 in which participants will start an openlabel 4-week intervention with metformin and the prebiotic MM.

Phase 1: This is a randomized double-blind cross-over study of youth with T2D with two intervention periods (metformin + prebiotic MM BiomeBliss® ®, and metformin + placebo). Participants will have 5 study visits over the 5-week period. After screening history and physical examination are performed at visit 1, participants will enter a 1-week run-in period in which metformin therapy will be discontinued and blood glucose will be monitored twice daily via finger stick or with a continuous glucose monitor. The order of intervention will be randomized at Visit 2; when initiating metformin, participants will have 1-3 days of dose escalation, then arrive at a final dose of 850mg twice daily. After 7-9 days of treatment, participants will be evaluated as described in Table 1, then enter a 2-week washout period of prebiotic/placebo and metformin, and then cross over to the opposite intervention for 1 week.

Phase 2: This is an open-label 4-week extension of metformin + prebiotic MM. Participants will receive a 1-month supply of metformin and prebiotic at the end of Phase 1 (Visit 5) and be evaluated for measures of stool metabolite and glycemia at the end of the trial (Visit 6).

Every effort will be made to adhere to the proposed timelines, but some flexibility is required for scheduling of other studies, unanticipated equipment maintenance, etc. Scheduling variations will not be reported.

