Participants will receive instructions on stool collection at home and stool collection kits - one to be mailed back to the study team for analysis prior to stopping their baseline metformin dose (unless they are able to provide a stool sample after consent while still at NIH), and one to collect a sample in the 24 hours prior to visit 2 if has a bowel movement. Patients will also be taught how to fill out daily surveys to assess GI symptoms (see details below). They will meet with a member of the nutrition team to select foods for their metabolic diet and to be educated on completing a 3-day food record. Participants will also be educated on foods we will ask them to avoid during the study, such as pre/pro-biotics (kombucha, kefir, yogurt, etc.) and foods containing non-nutritive sweeteners.

Period 1 (Drug-free run-in, Visit 2 and 3)

Drug-free run-in period: Participants will discontinue metformin for the 7-10 days preceding Visit 2, to assess their metabolic and gut microbiome response off anti-diabetic medications, as well as to wash out the immediate effect of metformin on the participants microbiota. The timing of this 1 week period was chosen because changes in gut microbiome have been observed in as little as 1 day and on average 1 week [33]. During this time, participants will complete daily GI symptom questionnaires and monitor their blood glucose and upload their readings daily while not taking metformin. Participants with persistently elevated fasting glucose readings and/or signs and symptoms of metabolic decompensation (e.g. vomiting, dehydration, lethargy, abdominal pain, ketonuria and acidosis) will be withdrawn from the study and restarted on his/her medication. During the drug-free run-in period, individuals who cannot either wear the continuous glucose monitor (CGM), or complete at least 2 finger stick blood glucose measurements daily will be withdrawn from the study.

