Visit 2: This visit will take place 7-10 days after discontinuing metformin. Study personnel will review dosing and the completeness of GI questionnaires, as well as glucose trends with the participants. Participants will leave with a study metformin supply from the NIH pharmacy, as well as bottles of either placebo or prebiotic for a 1 week +15% supply and be instructed to take metformin and the powder mixed with a shake provided by the study team at the same time twice daily, with the first dose given with dinner that evening. Participants will take metformin 850mg with dinner on day 1-3and the dose will be increased to 850mg with breakfast and with dinner on day 3 and thereafter. Participants will fill out daily GI symptom questionnaires and will be instructed to contact the NIH study team if they are unable to tolerate the medication. Participants will be provided with 1 week of food to take home and consume on the week prior to Visit 3. The NIH Clinical Center Metabolic Kitchen will pack out meals for 7 days. Energy provided will be estimated using Mifflin St Jeor equation and an activity factor of 1.3 [34]. Participants will also leave with an accelerometer to be worn around the wrist 24 hours/day during the period between visits 2 and 3.

Visit 3: Participants will return to the NIH CC 7-9 days after visit 2. Stool and urine sample collection and bottle/ pill counts and assessment of uneaten food will be performed, and the accelerometer will be returned. Participants will undergo a MMT (see description below). Completeness of GI symptom questionnaires and glucose trends will be reviewed.

Period 2 (Washout, Visit 4 and 5)

Participants will be instructed to stop taking all metformin and MM/placebo powder during the washout period between visit 3 and 4; instructions for CGM and hyperglycemia precautions that were given at the screening visit will be reviewed with the family. The 2-3 week washout was chosen to minimize any carry-over effects and has been optimal for detecting gut microbiota after discontinuing therapy [9, 27].

Visit 4: Visit 4 will occur at the NIH CC 14-24 days after the beginning of the wash out period; The NIH Clinical Center Metabolic Kitchen will pack out frozen and non-perishable items to provide meals for 7 days. Participants will also be asked to wear the accelerometer on wrist until they return for visit 5.

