Visit 5: Participants will bring a stool sample and study medications and have identical assessments as described in visit 3 above. They will also be reminded about keeping food records, which they will be asked to do prior to visit 6

Phase 2 (open-label study and Visit 6)

At the end of Visit 5, patients will leave with a 1-month supply of metformin and MM, to continue taking twice daily, as well as an accelerometer device daily for 4 weeks. **Final study Visit 6** – Participants will undergo assessments as outlined in Table 1 and receive counseling on resuming their medication regimen from prior to the study, as well as follow up nutrition counseling on healthy diet and lifestyle practices.

Rescue visit for GI intolerance

If participants are unable to tolerate 850mg twice daily during the study, they will be withdrawn from the study and have the option come in for a rescue visit, where they will provide a stool sample and obtain bloodwork. They will then be offered the opportunity to enter the open label arm using BiomeBliss® in combination with their highest tolerable metformin dose.

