- 2. Comparable non-nutritive sweetener (NNS) in placebo and BiomeBliss. The proposed placebo is sweetened with a non-nutritive sweetener rather than by sucrose alone to help keep the mass of each dose similar and isocaloric. We expect that stevia (a "natural" NNS) and the artificial NNSs, such as sucralose and acesulfame, will have comparable but negligible effects on glycemia in the short term [40]. However, we acknowledge that the effects of NNS on the microbiome is an emerging area of research. The data on the effects of non-nutritive sweeteners and their potential alterations of gut microbiota are controversial. Over the last decade, there is an increasing number of rodent and in vivo models indicating modest changes in gut phyla with NNS doses that far exceed the maximum acceptable daily intake [41-45]. The clinical impact of these changes is still unclear; human studies are scarce and conflicting. A handful of clinical trials, using acesulfame do not agree on whether this sweetener exerts a change in gut microbiota [46-48]. To our knowledge, there are no

human trials rigorously evaluating gut microbiome with stevia and sucralose [49]. Additionally, we expect that during the phase 2 when we expect to see changes in the microbiome, our participants will be consuming NNS in possibly higher quantities in their usual diet. We will be asking them to avoid diet sodas and other items known to be sweetened principally with NNS (see appendix G), but even foods that are not advertised as "diet" or low-sugar frequently contain NNS, so they will be impossible to avoid in a real-world study.

	BiomeBliss	Gatorade G2 Placebo Mixture
		(4g Grape + 15g Glacier Freeze)
Calories per serving	60kcal (27g)	63 kcal (19g)
Ingredients	Inulin, Blueberry Extract, Beta-glucan (oats), Soy Protein Isolate, Pomegranate Flavor, Xanthan Gum, Citric Acid, Stevia Extract	Glacier Freeze: sugar, citric acid, salt, sodium citrate, natural flavor, monopotassium phosphate, modified food starch, calcium silicate, sucralose, acesulfame potassium, blue 1 Grape: sugar, citricacid, salt, sodium citrate, monopotassium phosphate, natural and artificial flavor, cornstarch calcium silicate, sucralose, acesulfame potassium, blue 1, red 40
Dietary Fiber	9g	None
Total Carbohydrate	22g	17.5g

Table 2:	Biome	Bliss ar	nd G2	Placebo	Nutrition	Facts
	Dionic	Dii35 ui		I IUCCOC	Hatiltion	1 4010

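### Aim 2 compares the prebiotic with placebo on stool SCFA at 4 weeks, but nobody takes placebo for longer than 7 to 9 days

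*Combined protocol and SAP*

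**What the plan says.** Section 2.0, Aim 2, sets the SCFA comparison in participants "when treated with prebiotic MM vs. placebo after 1 week and 4 weeks", and its hypothesis again names placebo as the comparator. The exploratory aims contain a similar contrast for glucose, insulin and incretins: "after treatment with placebo compared to 4 weeks of continuous prebiotic MM intervention".

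Section 3.1 gives placebo one crossover period, assessed after 7 to 9 days. Of Phase 2 it says: "This is an open-label 4-week extension of metformin + prebiotic MM". Section 3.2 places its start directly after the crossover: "At the end of Visit 5, patients will leave with a 1-month supply of metformin and MM, to continue taking twice daily".

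On diet, section 3.2 (Visit 2) says: "Participants will be provided with 1 week of food to take home and consume on the week prior to Visit 3". The Visit 4 text arranges the same for Period 2, and Table 1 shows supplied meals only at Visits 2 and 4. For Phase 2, section 3.5 expects that "our participants will be consuming NNS in possibly higher quantities in their usual diet".

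Section 5.2 analyses SCFA change over 1 and 4 weeks by repeated-measures ANOVA. It does not say which visits form the 4-week contrast. Period and sequence are listed as covariates in the paragraph on the primary outcome; the SCFA paragraph does not mention them.

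**The concern.** A 4-week comparison with placebo needs a placebo response at 4 weeks, or at least a comparator alike in everything but MM. The design has neither. The protocol itself gives a reason to expect a difference without any MM effect; section 1.0 says: "While metformin alone can increase SCFA, prebiotic MM may be able to augment this increase". Aim 2 also describes SCFA as products of dietary fibre fermentation, so a change of diet bears directly on this outcome.

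If the 4-week part of Aim 2 is tested as worded, a higher SCFA at Visit 6 could be credited to MM when longer metformin, usual diet or elapsed time produced some or all of it. The reverse is also possible: a change of diet could hide an MM effect. SCFA is the only secondary outcome, so this bears on a headline conclusion. The primary outcome is not affected.

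**Working it through.** **The plan's own figure.** Section 5.1 states 90% power for SCFA with 20 participants, alpha 0.05 and correlation 0.5. With that correlation the SD of a paired difference equals the stated SD, since SD × √(2(1 − 0.5)) = SD. The normal approximation, two-sided, is power = Φ(√n × mean/SD − 1.96):

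- butyrate: √20 × 4.17/5.72 − 1.96 = 1.30, giving 90.3%
- propionate: √20 × 2.95/3.3 − 1.96 = 2.04, giving 97.9%

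The stated 90% reproduces on butyrate. These inputs are before-and-after changes over 3 months of metformin in 4 youths (section 1.0, Figure 3). They describe metformin, which is one of the confounders here, and not MM against placebo.

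**Exposure at the visits being compared** (sections 3.1 and 3.2, taking Phase 2 as 28 days):

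| | Placebo visit | Visit 6, MM-first | Visit 6, placebo-first |
|---|---|---|---|
| Unbroken metformin, days | 7–9 | (7–9) + 28 = 35–37 | 35–37 |
| Unbroken MM, days | 0 | 28 | (7–9) + 28 = 35–37 |
| Meals | supplied | usual diet | usual diet |
| Blinded, randomised | yes | no | no |

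The length of unbroken MM at Visit 6 also depends on sequence, although cumulative MM is about 5 weeks in both.

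**Can a model separate the effects?** Code the six cells:

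| Sequence, visit | Intercept | Sequence | Period 2 | 1-week MM | Visit 6 conditions | 4-week MM |
|---|---|---|---|---|---|---|
| MM-first, V3 | 1 | 0 | 0 | 1 | 0 | 0 |
| MM-first, V5 | 1 | 0 | 1 | 0 | 0 | 0 |
| MM-first, V6 | 1 | 0 | 0 | 0 | 1 | 1 |
| Placebo-first, V3 | 1 | 1 | 0 | 0 | 0 | 0 |
| Placebo-first, V5 | 1 | 1 | 1 | 1 | 0 | 0 |
| Placebo-first, V6 | 1 | 1 | 0 | 0 | 1 | 1 |

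Visit 6 conditions stand for longer metformin, usual diet and elapsed time together. The last two columns are identical, so the rank is 5 for 6 terms. The four Phase 1 rows with the first four columns have rank 4 of 4, so the 1-week MM effect is estimable. More participants add rows of the same kind and change nothing.

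**The stool sample taken on prior metformin.** Section 3.2 provides a collection kit, "one to be mailed back to the study team for analysis prior to stopping their baseline metformin dose". It does not supply the missing comparator: it is not randomised, prior dose varies between participants, and no analysis uses it.

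**Illustration only.** The documents give no SCFA time course for metformin alone. Assume that MM has no effect, that diet and time add nothing, and that the longer metformin adds a fraction f of the 3-month change in section 5.1. With a paired t-test (two-sided 0.05, SD of the difference equal to the stated SD), the chance of a significant result wrongly read as MM versus placebo is:

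| f | 20 participants, propionate / butyrate | 10 completers, propionate / butyrate |
|---|---|---|
| 0.1 | 6.7% / 6.1% | 5.7% / 5.5% |
| 0.25 | 15.8% / 12.1% | 9.7% / 8.1% |
| 0.5 | 47.5% / 34.0% | 24.4% / 17.8% |

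**Period term in the 1-week comparison.** Let τ be the MM effect and π the period effect. The within-person difference, MM minus placebo, has expectation τ − π in the MM-first sequence and τ + π in the placebo-first sequence. With n1 and n2 completers in the two sequences and no period term, the share of π entering the estimate is |n1 − n2|/(n1 + n2):

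- 5:5 gives 0/10 = 0%
- 6:4 gives 2/10 = 20%
- 7:3 gives 4/10 = 40%

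With a period term the estimate is the average of the two sequence means, [(τ − π) + (τ + π)]/2 = τ, so the share is 0% at every split. Section 5.1 assumes 50% attrition, so uneven completion is plausible.

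**The case against.** The strongest reply is that the 4-week placebo contrast is loose wording. The secondary objective in section 2.0 speaks of change after the MM intervention, section 2.1 names no comparator, section 5.2 specifies no placebo test at week 4, and Phase 2 is openly called an extension. Aim 2 could then mean placebo control at 1 week with MM followed to 4 weeks. That reading is possible, but Aim 2, its hypothesis and the exploratory aim all name placebo, so the text has to be settled either way.

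It can also be said that the rank result follows from the coding. That is true: it states formally that there is no 4-week placebo arm and measures no bias.

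On size, section 3.2 cites microbiome changes within a day and on average within a week. If SCFA behaved likewise, extra metformin time would matter less. But that citation concerns the microbiome, and section 3.5 expects microbiome changes in Phase 2, so the documents point both ways. The metformin effect on SCFA in section 1.0 rests on 4 youths with P=0.1. The values of f above are assumptions and carry no evidential weight. Food records are kept in Phase 2, but they would not remove the confounding.

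The period-term point is a separate matter from the 4-week contrast. Its uneven splits are hypothetical, and it vanishes at balance.

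**Conclusion.** The concern holds. The trial can estimate MM against placebo on SCFA at 1 week and cannot do so at 4 weeks. The same applies to the exploratory contrast of placebo with 4 weeks of MM. This follows from the treatment schedule and needs no numerical assumption; the day counts are approximate because section 3.1 allows scheduling flexibility. The size and direction of the confounding cannot be determined from the documents. Separately, the 1-week SCFA comparison is valid, but without a period term it would absorb 20% to 40% of any period effect at completer splits of 6:4 to 7:3. The size of that period effect is unknown.

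**What to change.** - **Aim 2, section 5.2 and the exploratory metabolic contrast:** limit MM-versus-placebo inference to the two randomised 1-week periods.
- **SCFA model:** use the primary outcome's linear mixed model, with treatment, period, sequence, the pre-period value (Visit 2 or Visit 4), a participant effect and all available samples. State how a missing pre-period sample is handled, so that it does not silently drop the post-treatment sample. Table 1 already schedules stool collection at both visits.
- **SCFA at Visit 6:** report it descriptively, with no MM-versus-placebo test, as an uncontrolled within-person change from the off-drug Visit 2 stool sample under metformin and MM combined.
- **Change from Visit 5, if shown:** present it by sequence, stating that Visit 5 is a placebo visit in the MM-first sequence and an MM visit in the placebo-first sequence.

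The cost is wording and model specification; no visits or samples are added. The trial gives up a 4-week placebo-controlled claim that its design cannot support.
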